4.1 Data and Safety Monitoring Committee

Data and Safety Monitoring will be conducted by the investigators and the Study Physician. They will review all possible Adverse Events (AEs) and Serious Adverse Events (SAEs). They will ensure that this information is captured in a comprehensive manner and reported according to Good Clinical Practice (GCP). The investigators, Study Physician, and the research staff will oversee and complete the monitoring process. Monitoring will be performed on an ongoing basis in accordance with the University of Pennsylvania Sponsor-Investigator Standard Operating Procedure PM 004.

The investigators are responsible for:

1. Obtaining IRB review and approval of a clinical investigation before the investigation is initiated and ensuring continuing review of the study by the IRB in accordance with 21 CFR Part 56;
2. Obtaining informed consent in accordance with 21 CFR Part 50; and
3. Assuring that all staff and subjects understand and accept the obligations incurred in undertaking this double-blind placebo-controlled study in accordance with 21 CFR Parts 312, 511, 812, 813 and any other applicable regulations.

The research staff is responsible for collecting and recording all clinical data. This includes ensuring that all source documents exist for the data on the Case Report Forms (CRFs), ensuring all fields are completed appropriately, and all corrections are done according to GCPs. Any inconsistencies/deviations will be documented on the CRFs and such findings will be reviewed at the weekly study meetings.

The Project Manager will oversee staff training. Training will include a review of the study protocol, informed consent, telephone screen, CRFs and the procedures that are in place regarding session check-in, data collection, data entry and quality control. All applicable regulations will be reviewed and the roles/responsibilities of each staff member will be explained. All questions will be answered and the training will be documented in a training log, which will be initialed by those involved. The Project Manager will also confirm all appropriate documentation of informed consent and storage of consents in a separate consent binder, and will maintain the study regulatory binder.

The Project Manager, PI ([name])/Co-I and Study Physician will work together to confirm eligibility criteria. The Study Physician/Nurse Practitioner and PI ([name])/Co-I will review charts for each subject and will document reviews by signing and dating the final eligibility checklist in each chart, and the medical history and physical form.

The research staff and Project Manager will ensure all medication is properly ordered and received from IDS, stored at the center, labeled, and distributed to subjects.

The data managers will be responsible for creating all CRFs and ensuring that all data will be entered and stored in a manner consistent with the design of the approved CRFs. They will also be responsible for developing the data entry/quality control producers for this study.

Enrollment will be complete when 84 subjects complete all study requirements. On average, 3-4 subjects will be enrolled per month. During the course of the study, safety and data quality monitoring will be performed on an ongoing basis in accordance with the University of Pennsylvania Sponsor-Investigator Standard Operating Procedure PM 004 and any

findings will be reviewed on a regular basis with the Investigators at the regular study meeting. The monitoring will include a regular assessment of the number and type of serious adverse events. The first monitoring day will occur no more than two weeks after the first subject is entered.

4.2 Adverse Event Reporting and Monitoring

Adverse Event (AE)

An Adverse Event (AE) is a subcategory of the broader category of "Unanticipated Problems Posing Risk to Subject or Others." An adverse event is defined as:

- Any unfavorable or unintended sign (including an abnormal laboratory finding), symptom, or disease occurring at any stage of the study
- Abnormal results of diagnostic procedures are considered to be adverse events if the abnormality:
 - results in study withdrawal
 - is associated with a serious adverse event
 - is associated with clinical signs or symptoms leads to additional treatment or to further diagnostic tests
 - is considered by the investigator to be of clinical significance
- May include an exacerbation of a pre-existing condition, intercurrent illness or injury, drug interaction, drug overdose, failure of expected action or significant worsening of the disease under study
- An event that may compromise the rights, safety, or welfare of research subjects

Any event that could be characterized by the definitions above is an AE whether or not considered related to the study or product.

Serious Adverse Event (SAE)

Adverse events are classified as serious or non-serious. A **serious adverse event** is any AE that is:

- fatal
- life-threatening
- requires or prolongs hospital stay
- results in persistent or significant disability or incapacity
- a congenital anomaly or birth defect
- an important medical event

Important medical events are those that may not be immediately life threatening, but are clearly of major clinical significance. They may jeopardize the subject, and may require intervention to prevent one of the other serious outcomes noted above. For example, drug overdose or abuse, a seizure that did not result in in-patient hospitalization, or intensive treatment of bronchospasm in an emergency department would typically be considered serious.

All adverse events that do not meet any of the criteria for serious will be regarded as **non-serious adverse events**.

Adverse Event Reporting Period

The study period during which adverse events must be reported is the period from the initiation of any study procedures to the end of the study treatment follow-up. For this study, the study treatment follow-up is defined as 7 days following the last administration of study treatment. A compilation of any Adverse Events will be provided in the annual and final progress reports to NIDA.

Preexisting Condition

A preexisting condition is one that is present at the start of the study. A preexisting condition will be recorded as an adverse event if the frequency, intensity, or the character of the condition worsens during the study period.

General Physical Examination Findings

At screening, any clinically significant abnormality will be recorded as a preexisting condition. At the end of the study, any new clinically significant findings/abnormalities that meet the definition of an adverse event must also be recorded and documented as an adverse event.

Post-study Adverse Event

All unresolved adverse events will be followed by the investigators until the events are resolved, the subject is lost to follow-up, or the adverse event is otherwise explained. At the last scheduled visit, a research team member will instruct each subject to report any subsequent event(s) that the subject, or the subject's personal physician, believes might reasonably be related to participation in this study.

Hospitalization, Prolonged Hospitalization or Surgery

Any adverse event that results in hospitalization or prolonged hospitalization will be documented and reported as a serious adverse event unless specifically instructed otherwise in this protocol. Any condition responsible for surgery should be documented as an adverse event if the condition meets the criteria for an adverse event.

Neither the condition, hospitalization, prolonged hospitalization, nor surgery are reported as an adverse event in the following circumstances:

- Hospitalization or prolonged hospitalization for diagnostic or elective surgical procedures for a preexisting condition. Surgery will **not** be reported as an outcome of an adverse event if the purpose of the surgery was elective or diagnostic and the outcome was uneventful.
- Hospitalization or prolonged hospitalization required to allow efficacy measurement for the study.
- Hospitalization or prolonged hospitalization for therapy of the target disease of the study, unless it is a worsening or increase in frequency of hospital admissions as judged by the clinical investigator.

Medical and scientific judgment should be exercised in deciding whether expedited reporting is appropriate in other situations, such as important medical events that may not be immediately life-threatening or result in death or hospitalization but may jeopardize the patient or may require intervention to prevent one of the other outcomes listed in the definition above. These should also usually be considered serious. Other kinds of events can be labeled "serious adverse events" at the discretion of the investigator.

To ensure no confusion or misunderstanding of the difference between the terms "serious" and "severe," which are not synonymous, the following note of clarification is provided: The term "severe" is often used to describe the intensity (severity) of a specific event (as in mild, moderate, or severe myocardial infarction); the event itself, however, may be of relatively minor medical significance (such as severe headache). This is not the same as "serious," which is based on patient/event outcome or action criteria usually associated with events that pose a threat to a patient's life or functioning. Seriousness (not severity) serves as a guide for defining regulatory reporting obligations.

Severity Grading Scale for Adverse Events

- Mild: Noticeable to the subject, does not interfere with the subject's daily activities, usually does not require additional therapy, dose reduction, or discontinuation of the study.
- Moderate: Interferes with the subject's daily activities, possibly requires additional therapy, but does not require discontinuation of the study.
- Severe: Severely limits the subject's daily activities and may require discontinuation of the study. This would include all adverse events defined as "serious adverse events".

Attribution/Association with the Drug or Intervention:

An assessment of the relationship between the adverse event and the drug/intervention will be made for each occurrence by an investigator.

Adverse Event Attribution Categories:

- Unrelated - The AE is clearly NOT related to the intervention

- Possibly - The AE may be related to the intervention
- Probably - The AE is likely related to the intervention
- Definitely - The AE is clearly related to the intervention

4.3 Recording of Adverse Events

At each contact with the subject after the Intake, the study research assistant will seek information on adverse events by specific questioning using a side effect checklist and, as appropriate, by examination. Side effects will be monitored through a two-pronged approach. First, participants will complete a side effects checklist (SEC) at each study visit after the Intake reporting with a frame of reference since their last study visit. The SEC will assess the frequency and severity of common side-effects associated with metformin. These items will be rated by participants on a 0 (none) to 3 (severe) scale, and can be summed to provide an overall side effects index. Participants will also complete a non-structured, open-ended question (SEC Open-ended) at each study visit with a one week frame of reference to assess if participants are experiencing any additional symptoms or medical concerns that may be related to their participation in the study. Trained staff will review participant responses and collect additional information as needed from the participant.

Research staff are trained to inquire (time of onset, nature of issue reported, possible relation to metformin treatment, review of previously reported side effects or concerns, etc.) about any notable side effects or medical concern reported by participants. Any severe (or a pattern of moderate) side effects or notable medical concern will be reported to the Project Manager, Study Physician, and PI/Co-I to determine a course of action (e.g. continue to monitor, reduce medication, stop medication). This consult, including all relevant information, will be documented via email. The Study Physician is knowledgeable of side effects related to metformin and is qualified to manage possible side effects.

Based on published reports using the 500 and 1500 mg doses of metformin we expect few side effects and we expect these side effects to be mild and transient in nature. However, in the unlikely event of an adverse event (AE) the study physician/investigator will determine the severity of the AE, the relationship of the event to the study drug and decide the course of action for the study subject. The study physician/investigator will determine the relationship of toxicity of the study medication as not related, possibly related, probably related, or definitely related using standard criteria.

All adverse events occurring during each study period will be recorded. The clinical course of each event will be followed until resolution, stabilization, or until it has been determined that the study treatment or participation is not the cause. Serious adverse events that are still ongoing at the end of the study period must be followed up to determine the final outcome. Any serious adverse event that occurs after the study period and is considered to be possibly related to the study treatment or study participation will be recorded and reported immediately.

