This is a randomized, double-blind placebo-controlled, parallel arm pilot study of the effects of a low vs. high dose of metformin on abstinence-induced negative mood and cognitive deficits. Participants will complete Intake tasks to determine final eligibility before being enrolled into the study. Study visits will be completed either in-person at our center, or remotely (via phone or videoconferencing). Once eligibility is confirmed, subjects will attend a clinic visit (day 0) to establish baseline smoking rate, mood, and cognition. Subjects will then be randomized to one of three groups (low dose: 500 mg, high dose: 1500 mg, or placebo) and will complete 4 additional sessions (days 7, 14, 21, 23) to assess side effects, smoking rate, mood, craving, and withdrawal (Figure 1). Cognitive function will also be assessed on days 21 and 23. Subjects will be instructed to refrain from smoking for 24 hours prior to the laboratory session on day 23.

2. Study Visits

- **Telephone Screening.** Recruited subjects will complete an initial eligibility assessment in the HIV/AIDS clinic or over the telephone. This assessment reduces the likelihood that participants attend an Intake Session only to learn that they are ineligible or to allow us to ascertain physician's clearance should the participants have a medical condition that requires approval (e.g., mild hypertension). If a potential participant cannot be reached by phone, staff may send a text for the purposes of scheduling an initial eligibility screening phone call. This will help to reach potential participants who express interest in the study but do not answer phone calls from unrecognized numbers or do not regularly listen to voicemail messages. Texts will be sent from a central study account and not from the personal cellphones of any research staff. Participants who are initially eligible will be screened against our registration database to confirm that they are not currently participating in another research study at our Center and have not previously reported a condition or circumstance that would make them ineligible for the current study. Those participants who remain initially eligible will move forward with eligibility-determining tasks as part of the Intake session, which will be completed remotely and in-person. The Intake session must occur within 60 days of the initial eligibility screening or the participant will have to be re-screened.

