This session can be scheduled any time of day. However, the timing of this session will influence when the Day 21 and Day 23 testing appointments are scheduled. Ideally, the subsequent testing sessions would be at the same time of day but can be scheduled up to 3 hours earlier or later than the Baseline session. However, the sessions may go beyond 3 hours as determined by PI/Co-I discretion.

- Remote Check-In(Days 7 and 14). These sessions will be completed remotely via phone or videoconference and will last about 20 minutes. Participants will be asked to:

1. Report their smoking rate (timeline followback; TLFB)
2. Report their medication adherence
3. Report side effects and complete a concomitant medication review
4. Complete measures for mood, smoking urges, withdrawal symptoms, and subjective effects
5. Complete the MADRS, YMRS, Bipolar Disorder Additional Screener, if necessary
6. Review instructions for medication

This visit can be scheduled any time during the day and can be moved by plus or minus 1 day to accommodate for participant's schedule.

- Pre-Quit Testing Day (Day 21). Participants will be asked to bring their study medication to this visit. During this 2-hour visit, participants will complete the same activities they completed at the Baseline Session except that they will complete additional measures of pill count.

- Mandatory 24-H Abstinence Period. On Day 22, participants will receive a telephone call to remind them to begin their practice quit attempt approximately 24 hours before their scheduled 24-H testing session on Day 23. Participants will also be reminded that in order to remain eligible for the study, they must remain abstinent during this 24-hour period.

- 24-H Testing Day (Day 23). The 24-H Testing Day occurs after approximately 24 hours of abstinence from nicotine. The Testing Day Visit takes about 2 hours to complete and is split into two parts. The procedures participants will complete within each part of the Testing Day Visit are as follows:

- 24-H Testing Day Part 1

On Day 23 Part 1, participants will provide:

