Potential participants will be contacted over the phone after responding to recruitment advertisements. Participants will undergo an initial phone screening where preliminary eligibility for the research study will be determined. Only if a participant is initially eligible, will they complete Intake tasks to confirm eligibility. All data collected over the phone and during in-person visits will be collected by research staff who have completed the CITI Protection of Human Subjects Research Training as well as HIPAA Compliance Training. Information will never be recorded with identifiers other than study ID. A separate list of names with ID numbers will be accessible only by authorized personnel. All records will be kept in locked filing cabinets to maintain confidentiality. Results will not be communicated to other personnel or to the subjects. All analyses will be conducted on de-identified data. Data will be accessible to the Study Investigators, Study Physician, study staff, UPenn IRB, Office of Clinical Research, authorized UPenn staff (e.g. accounting and billing matters, provide treatment, etc.) and the Food and Drug Administration.

6. Tissue Specimens

Urine. A urine sample will be required at Intake and all testing sessions (Baseline, day 21 and day 23) for the drug and pregnancy screening. Participants who test positive for study prohibited drugs use may be deemed ineligible. Participants believed to have a false-positive result may continue in the study, with investigator approval. All female participants of child-bearing potential will complete urine pregnancy tests.

Blood. One 8.5 mL sample of blood will be drawn at the Intake visit to evaluate liver and renal function. At the Baseline and Pre-Quit Testing visits four samples (two 10 ml and two 8.5 ml) will be drawn to assess neuroinflammatory markers. A drop of blood (approximately 0.3 microliter) will also be collected at each visit following the Intake to assess blood glucose levels.

RISK/BENEFIT ASSESSMENT

1. Potential Study Risks

Potential Risks of the Medication: The following are the common side effects that have been reported with metformin XR treatment: diarrhea, nausea, and vomiting. Diarrhea led to discontinuation in 0.6% of patients. Side effects will be assessed at baseline and each subsequent visit (a total of 5 times throughout the study).

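### The one-week recall for unlisted symptoms does not match the visit intervals, and new events in the 7 post-dose days of the adverse event period rely on participants volunteering those they think related

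*Combined protocol and SAP*

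**What the plan says.** Section 4.3 (Recording of Adverse Events) uses two instruments at every visit after Intake. The checklist of common metformin effects is completed "reporting with a frame of reference since their last study visit". The open-ended question on other symptoms is put "at each study visit with a one week frame of reference to assess if participants are experiencing any additional symptoms".

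Baseline is Day 0, with later sessions on Days 7, 14, 21 and 23. Under Study Visits, a Day 7 or Day 14 check-in "can be moved by plus or minus 1 day to accommodate for participant's schedule". No day window is given for Days 21 and 23.

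Section 4.2 (Adverse Event Reporting Period) sets the reporting window as "the period from the initiation of any study procedures to the end of the study treatment follow-up", where "the study treatment follow-up is defined as 7 days following the last administration of study treatment". The same section counts an event as adverse regardless of relatedness. Its paragraph on post-study events, however, has staff tell participants at the last scheduled visit to report later events that they or their physician "believes might reasonably be related to participation in this study". Section 2.1 (Post-Study Follow-up) allows later contact only to clarify data already collected.

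**The concern.** The open-ended item is the only scheduled question aimed at symptoms that are not on the checklist. A fixed one-week recall matches the visits only when they are exactly 7 days apart. Longer intervals leave days unasked, and the 2-day interval before Day 23 produces overlap.

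The second problem does not depend on visit windows. The plan defines an adverse event period that outlasts its last contact, and then narrows what participants are asked to report in it. Section 4.3 says that all adverse events in the study period will be recorded, and the procedures do not fully deliver that.

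The Background section includes an exploratory aim: whether 1500 mg adds benefit over 500 mg without matching adverse effects. Adverse event capture supplies the data for the second half of that question.

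**Working it through.** **Inputs.** Recall of the open-ended item: 7 days (section 4.3). Visit days 0, 7, 14, 21, 23 (Design). Window of 1 day either way for Days 7 and 14 (Study Visits). Post-dose follow-up: 7 days (section 4.2). Dosing Days 1 to 23, taken with the evening meal (Design; Drugs or Devices).

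**Plan's own count.** Potential Study Risks says that side effects are assessed "a total of 5 times throughout the study". Days 0, 7, 14, 21 and 23 make 5, so the figure is reproduced.

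**Unasked days between visits.** For each interval, unasked days = max(0, interval − 7). The nine permitted schedules give:

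| Check-in days | Intervals from Day 0 | Unasked days |
|---|---|---|
| 6, 13 | 6, 7, 8, 2 | 1 |
| 6, 14 | 6, 8, 7, 2 | 1 |
| 6, 15 | 6, 9, 6, 2 | 2 |
| 7, 13 | 7, 6, 8, 2 | 1 |
| 7, 14 | 7, 7, 7, 2 | 0 |
| 7, 15 | 7, 8, 6, 2 | 1 |
| 8, 13 | 8, 5, 8, 2 | 2 |
| 8, 14 | 8, 6, 7, 2 | 1 |
| 8, 15 | 8, 7, 6, 2 | 1 |

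Eight of nine schedules lose 1 or 2 days in total; only the exact nominal one loses none. If one check-in is missed and the other visits are on nominal days, the interval is 14 days and 14 − 7 = 7 days are unasked.

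**Overlap on Day 23.** Overlap = 7 − (23 − 21) = 5 of the 7 recall days, under every schedule.

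**Post-dose tail.** The end of the period is the last dose day + 7. The Day 23 dose may follow the Day 23 visit, so both cases are shown:
- last dose Day 23: the period ends on Day 30; 30 − 23 = 7 days after the last visit; 7/30 = 23%
- last dose Day 22: the period ends on Day 29; 29 − 23 = 6 days; 6/29 = 21%

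**Side result, not in the totals above.** The period opens with the first study procedure, and up to 30 days may separate Intake and Baseline. A one-week question at Baseline can then leave 30 − 7 = 23 pre-dose days unasked. These days do not bear on tolerability, but the same wording change covers them.

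**The case against.** The plan has real safeguards, and several stronger readings do not survive them.

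- **That events are missed or double-counted.** A reader might infer this, but the text supports only that they can be missed or reported twice. Section 4.3 has staff ask time of onset and review earlier reports, so a repeated mention can be recognised. What stands is that no explicit rule for merging repeats is written.
- **That the open-ended item is the only route for unlisted events.** Section 3.2 gives participants written instructions to call about severe side effects or adverse events between visits. Section 4.3 also has staff enquire at each contact. It is the only scheduled question aimed at such symptoms, which is a narrower statement.
- **That the gaps fall on the dose step-ups.** The unasked days come just after the earlier visit: Day 1, Days 7 to 8, or Day 14. The high-dose arm steps up on Days 8 and 15, in the evening. Only Day 8 can coincide, and within the permitted windows no 1500 mg day before Day 23 goes unasked.
- **That people who stop early have no later scheduled contact.** The documents do not say that stopping medication ends visits, and section 4.2 has unresolved events followed. What stands is that the post-study instruction is tied to the last scheduled visit, which someone who leaves early may not attend.

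It is also fair that the checklist covers the listed metformin effects without gap or overlap between visits, that all blinded arms share one schedule, and that this is a small pilot with no formal testing. These points limit the size of the between-visit problem. They do not touch the post-dose week: self-report there is passive, and the last-visit instruction is narrower than the plan's own definition.

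**Conclusion.** The point holds as an internal inconsistency with modest consequences. Between Baseline and Day 23, unlisted symptoms go unasked for 0 to 2 days per participant if all check-ins take place, and for about 7 if one is missed. Five of the seven days recalled on Day 23 are asked about twice. After Day 23, 6 to 7 of about 29 to 30 days rest on passive self-report limited to events thought related. This last part is the more important, because it affects every participant who completes the study and needs no visit to move.

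Assumptions: Days 21 and 23 are taken as fixed, and the Day 22 reminder call is not counted as an adverse event contact (counting it would not change the gaps). The documents give no rate of moved or missed check-ins, so how often the between-visit gaps would arise cannot be estimated.

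**What to change.** 1. Word the open-ended question as *since your last completed visit*, and use the same frame for the checklist. Unasked days between Baseline and Day 23 fall to 0, including after a missed check-in, and the Day 21/Day 23 overlap falls from 5 days to 0. The cost is the wording of one item.
2. Reconcile the two paragraphs of section 4.2. At the last visit attended, including an early withdrawal visit, tell participants to report all events, related or not, through 7 days after the last dose. The cost is one changed instruction.
3. Optionally, add a short remote check at the end of that week in the existing check-in format. This would turn passive capture into a scheduled question; its downside is one more contact per participant. The first two changes are worth making without it.
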